A single-center prospective randomized controlled pilot trial was conducted at the Presley Regional Trauma Center at Regional One Health in Memphis, TN from 1/1/16 to 12/13/17. This hospital is the only trauma center in Memphis, serves as the only trauma center in the Mid-South area, and is a major teaching facility for the University of Tennessee Health Science Center. The Mid-South is a geographic area of approximately 3,500 square miles surrounding Memphis including western Tennessee, eastern Arkansas, northern Mississippi, and small portions of Missouri and Kentucky. The trial is registered on clinicaltrials.gov (NCT02957331). After informed consent was obtained by one of the investigators or research nurses from the patient or legally authorized representative (LAR), patients were randomly assigned to either the treatment (PRO) or control arm using block randomization in groups of 4 to ensure equal group size. This sequence was generated using SAS version 9.4 (SAS Institute, Cary, NC). The study was not blinded due to the treatment effects and need for titration of the medication on physiologic parameters.

The primary outcome was in-hospital mortality. The secondary outcome was to examine the interaction between beta-blockade and catecholamines by measuring urinary catecholamines. A power analysis was performed using literature review to determine probable effect size. Utilizing a 15% difference in mortality between groups, a sample of 99 patients per group would be required to power the study at 0.80. This sample size would not be feasible at a single center. Therefore, in lieu of performing a multi-center study with limited resources, we elected to perform a pilot study to determine study

safety, feasibility, and effect size over a one-year period. The enrollment was re-assessed after one year and still short of the goal, so the study was extended an additional year.

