Eligible patients for screening were 18 years or older with a TBI as determined by Glasgow Coma Scale score (GCS) less than 12 on admission and documented brain injury on head computed tomography scan. Qualifying patients were randomized within 72 hours of injury. Exclusion criteria included patients with a significant injury in another body region (Abbreviated Injury **Scale score** >3), incarceration or gravidity, hepatic disease, home beta-blocker use, ongoing resuscitation or vasoactive medications, active acute coronary syndrome, and **non-survivable injury as determined by neurosurgery review of imaging**. Data were extracted from the electronic medical record (Sorian, Cerner, Kansas City, MO) and the local trauma registry (NTRACS version 3.0, Digital Innovations, [name]). Patients assigned to the PRO arm were dosed with propranolol starting at 20 mg three times daily (TID) by mouth or per feeding tube. The dose of propranolol was increased daily in 20 mg TID increments (60 mg/day total) until heart rate (HR) was less than 100 beats per minute (bpm) with maximum dose of 640 mg/day. Parameters for holding the medication included HR less than 60 bpm or systolic blood pressure less than 100 mm Hg. Patients assigned to the control arm were managed per institutional standard for TBI based on the Brain Trauma Foundation guidelines.²⁷ Neither arm had additional beta-blockers withheld if the care team deemed that class of medication necessary for appropriate care. Treatment duration for active study intervention was 14 days with a 48-hour taper of propranolol after the study period ended in the PRO arm. Patients were followed during the hospital stay until death or discharge.

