Variables collected included demographics, severity of injury, severity of illness scores, physiologic parameters, operative interventions, hospital length of stay (LOS), intensive care unit length of stay (ICU LOS), discharge disposition, infectious morbidity, urinary catecholamines, and mortality. Urinary catecholamines were collected from discarded urine at study enrollment and then at study day (SD) 2, SD-5, SD-7, SD-10, and at the end of the study period (SD-14) or when the patient came off study. The samples were stabilized with hydrochloric acid (HCl) and sent to a standard lab. Timely acid stabilization of the urine specimens was required prior to shipping to the central lab for processing. If HCl was not added to the specimen, unpredictable results were obtained that were not physiologically possible *in vivo*. These values were excluded from analysis. Patients in the PRO arm were compared to the control **using intent to treat analysis.**

Statistical analyses for categorical variables were compared using *Chi*-square tests or Fisher's exact tests where appropriate. Normally distributed continuous variables were compared using *Student's* t-tests and non-normally distributed continuous variables were compared using Wilcoxon Rank Sums tests. Effect size for mortality was calculated using the absolute difference between treatment groups. A two-way mixed model III Analysis of the Variance (ANOVA) with repeated measures was used to estimate differences between the two treatment arms over time. Using planned contrasts, the mean for each follow-up measurement was compared to SD-1 (i.e., randomization) for *within-group* contrasts and means at each assessment time were compared for *between-group* contrasts. Because these contrasts were planned, no correction was made for multiple comparisons. Output for the ANOVA is reported as Least Square Means

(LSMeans) with standard error (\pm SE). Finally, Kaplan-Meier survival analysis was performed to further examine mortality over time between groups. All statistical analyses were performed using SAS 9.4 (SAS Institute, Cary, NC). The University of Tennessee Health Science Center and Regional One Health Institutional Review Boards approved the study. A *p* value of less than 0.05 was considered significant.

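### The supplementary Kaplan-Meier analysis has no rule for live discharge; if discharges are censored, its curves can overstate in-hospital mortality but never understate it

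*Combined protocol and SAP*

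**What the plan says.** The design text sets the endpoint: "The primary outcome was in-hospital mortality". The paragraph on eligibility, treatment and follow-up sets the observation window: "Patients were followed during the hospital stay until death or discharge". No contact after discharge and no fixed horizon are described.

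The statistical analysis paragraph gives the effect measure: "Effect size for mortality was calculated using the absolute difference between treatment groups". It assigns categorical variables to chi-square or Fisher's exact tests. It then adds: "Finally, Kaplan-Meier survival analysis was performed to further examine mortality over time between groups". For that last analysis it gives no time origin, censoring rule, between-arm test or competing-risk method.

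The data collected include length of stay in hospital and in intensive care, and also "discharge disposition, infectious morbidity, urinary catecholamines, and mortality".

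**The concern.** A Kaplan-Meier curve cannot be drawn without deciding what happens when a patient leaves hospital alive. Since observation stops there, censoring at discharge is the natural reading, although the documents do not say so.

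Kaplan-Meier assumes that a censored patient remains exposed to the same future risk as those still under observation. A discharged patient can no longer die in hospital during that admission. Censoring at discharge therefore gives the probability of death in a hypothetical setting where nobody is ever discharged. It does not give the proportion who die in hospital.

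Two readings of the plot are at stake:

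- **Curve height.** It can end at a mortality figure above the trial's own primary-outcome proportion.
- **Gap between arms.** If discharge rates differ by arm, the gap between the curves need not match the gap in in-hospital death. This matters because the pilot is meant, among other things, to give an effect size.

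**Working it through.** The plan gives no Kaplan-Meier figure, so there is none to reproduce. The check has four parts: the direction of the discrepancy, its possible size in one arm, its effect on the contrast between arms, and the validity of a log-rank test.

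**1. Direction.** Let hd(t) and hx(t) be the daily hazards of in-hospital death and live discharge, with discharges censored.

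- 1−KM(t) = 1 − exp(−∫hd), which equals ∫ exp(−∫hd)·hd.
- Cumulative incidence: CIF(t) = ∫ S·hd, with S = exp(−∫(hd+hx)).

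Because exp(−∫hx) ≤ 1, CIF(t) ≤ 1−KM(t) at every time. In a sample, the two are equal until a death follows a discharge. In 2,000 simulated arms of 30 patients, 1−KM was never below the CIF, and the final CIF always equalled the crude proportion dying in hospital. In one simulated cohort of 100,000, day-30 mortality was 25.4% with discharges censored. It was 18.4% both by CIF and with discharged patients carried event-free.

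**2. Size in one arm.** Every rate here is an assumption. Eventual in-hospital mortality is set at 20%, and live discharge at 0.06/day once it begins.

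- (a) Death hazard decays with a 5-day time constant; discharges start on day 7. Solved initial death hazard: 0.0473/day.
- (b) 10-day time constant; discharges start on day 3. Initial hazard: 0.0312/day.
- (c) Constant, fully overlapping hazards, an extreme case. Death hazard: 0.0150/day.

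Day 30, with the numbers put in:

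- (a) 1−KM = 1 − exp(−0.0473×5×(1−e^−6)) = 21.0%.
- (b) 1−KM = 1 − exp(−0.0312×10×(1−e^−3)) = 25.7%.
- (c) 1−KM = 1 − exp(−0.015×30) = 36.2%; CIF = (0.015/0.075)×(1 − exp(−0.075×30)) = 17.9%.

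The CIF in (a) and (b) was integrated numerically (trapezoid rule, 0.005-day grid).

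| Setting | Day 14: 1−KM | CIF | Excess (points) | Day 30: 1−KM | CIF | Excess (points) |
|---|---|---|---|---|---|---|
| (a) | 19.9% | 19.4% | 0.5 | 21.0% | 20.0% | 1.0 |
| (b) | 21.0% | 18.1% | 2.9 | 25.7% | 19.9% | 5.8 |
| (c) | 18.9% | 13.0% | 5.9 | 36.2% | 17.9% | 18.3 |

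**3. Contrast between arms at day 30.** Discharge is assumed at 0.06/day in one arm and 0.04/day in the other.

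*Equal eventual mortality, 20% in both arms.* The initial death hazards at discharge 0.04/day are 0.0466, 0.0286 and 0.0100 per day. The last column is taken from unrounded values.

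| Setting | 1−KM | CIF | 1−KM gap minus CIF gap (points) |
|---|---|---|---|
| (a) | 21.0% v 20.7% | 20.0% v 20.0% | 0.3 |
| (b) | 25.7% v 23.8% | 19.9% v 19.7% | 1.8 |
| (c) | 36.2% v 25.9% | 17.9% v 15.5% | 8.0 |

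*Equal death hazard.* The Kaplan-Meier curves are then identical in the two arms, but in-hospital mortality is not.

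| Setting | CIF | Gap the curves hide (points) |
|---|---|---|
| (a) | 20.0% v 20.3% | 0.3 |
| (b) | 19.9% v 21.4% | 1.5 |
| (c) | 17.9% v 22.0% | 4.1 |

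**4. Log-rank test.** The plan names no test for the curves. If a log-rank test with censoring at discharge was used, it keeps its level for the cause-specific hazard of death in hospital. With equal death hazard 0.015/day and discharge 0.06 v 0.04/day, 10,000 simulated trials rejected in 5.3%, 5.0% and 4.8% of runs at 25, 50 and 99 patients per arm.

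**The case against.** The strongest reply is that no wrong analysis has been shown, only an unstated rule. The discrepancy needs two steps that the documents do not contain: discharges must have been censored, and someone must then read the height of the curve as in-hospital mortality. The stated purpose is a further look at mortality between groups. The primary outcome is a proportion that is fully observed by death or discharge, and neither its test nor its effect size comes from the curves. The illustrative rates have no anchor in the plan, and the largest figures come from a setting that is extreme by construction. The quoted sentence also says mortality, not in-hospital mortality. If overall mortality was meant, the problem would be loss to follow-up, and carrying discharged patients event-free would assume that none die later.

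Most of this stands as a limit on weight. It does not remove the point. Whichever rule was used decides what the curve estimates, and the reader cannot tell which it was. Given the endpoint and the observation window, in-hospital death is the only mortality the trial can describe, and the remedy is confined to it. If deaths do come early, setting (a) shows that the effect is small, but nothing in the documents establishes that they do.

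**Conclusion.** The concern holds, as a minor point about a supplementary analysis. The missing discharge rule is a fact of the text. The inequality is exact if discharges are censored, and there is no excess if they are carried event-free.

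The true size is unknown. Under the assumed rates with earlier deaths, (a) and (b), the day-30 excess in one arm is 1.0 to 5.8 points and the distortion between arms is about 0.3 to 2 points. The larger values, 18.3 points in one arm and 4.1 to 8.0 points between arms, need death and discharge to overlap heavily throughout the stay.

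The chi-square or Fisher comparison and the planned absolute difference are untouched. Confidence is medium, because the bias depends on a censoring rule that has to be inferred.

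**What to change.** State the time origin (randomization), the horizon and how live discharges enter the curve. Then do one of the following:

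- **Preferred:** show the cumulative incidence of in-hospital death from randomization by the Aalen-Johansen estimator, with live discharge as a competing event.
- **Equivalent for this endpoint:** carry patients discharged alive as event-free to a horizon covering the longest stay, so that the curve ends at the in-hospital proportion. Say plainly that this describes in-hospital death only, since survival after discharge is not observed.
- **If Kaplan-Meier with censoring at discharge is kept:** label it, and any log-rank test, as a comparison of cause-specific hazards, and do not read one minus the curve as in-hospital mortality.

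The cost is a sentence or two and a re-run on length of stay, discharge disposition and mortality, all already collected. No further patients or follow-up are needed. The new curves will usually show lower mortality than censored Kaplan-Meier curves would, which should be explained if censored curves have already been presented.
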